7.1.4.1 Replacement policy

Not applicable.

7.1.5 Withdrawal of Consent

Patients may voluntarily withdraw consent to participate in the study for any reason at any time. Withdrawal of consent occurs only when a patient does not want to participate in the study any longer, and does not want any further visits or assessments, and does not want any further study related contact.

Novartis will continue to retain and use all research results that have already been collected for the study evaluation. All biological samples that have already been collected may be retained and analyzed at a later date (or as required by local regulations).

If a patient withdraws consent, the investigator should make reasonable effort (e.g. telephone, e-mail, letter) to determine the primary reason for this decision while respecting the subject's rights and record this information.

Study drug must be discontinued and no further assessments conducted.

Further attempts to contact the patient are not allowed unless safety findings require communication or follow-up.

7.1.6 Follow-up period

All patients must have safety evaluations performed approximately 30 days after the last dose of study drug. Patients who discontinue study drug before the Week 12 visit must perform scheduled post-treatment follow-up visits through and including Week 12 (± 3 days) as indicated in [Table 7-1a](#) and [Section 7.1.4](#). If the 30 day follow-up evaluations should occur at the time of a scheduled visit; any assessments common to both visits only need to be performed once.

Data collected should be added to the Adverse Events eCRF and the Concomitant Medications eCRF.

7.1.7 Lost to follow-up

For patients whose status is unclear because they fail to appear for study visits without stating an intention to withdraw consent, the investigator should show "due diligence" by contacting the patient, family or family physician as agreed in the informed consent and by documenting in the source documents steps taken to contact the patient, e.g. dates of telephone calls, registered letters, etc. A patient should not be considered lost to follow-up until due diligence has been completed. Patients lost to follow-up should be recorded as such on the appropriate Disposition eCRF.

7.2 Assessment types

7.2.1 Efficacy assessments

Table 7-3 Disease and Imaging Assessment collection plan

Procedure	Screening	During Treatment/Follow-up
24-hour urine samples to test for Urine Free Cortisol and creatinine	Mandated at screening (post washout)	Mandated for Periods 1 and 2, the optional Extension and the 30 day Post Treatment Follow-up, as detailed in Table 7-1a , Table 7-1b and Table 7-2 . *Every effort should be made to collect samples for patients discontinuing treatment prior to Week 12 during Period 1 per Table 7-1a . Three 24-hour samples are to be collected at screening, Day 1, Week 12, Week 36, Week 48 and Week 12 Post-Treatment follow-up visit. Two 24-hour samples are to be collected at all other study time points.
Physical features of CD	Mandated at screening	Mandated for Periods 1 and 2, the optional Extension and the 30 day Post Treatment follow-up, as detailed in Table 7-1a , Table 7-1b and Table 7-2 .
DXA scan (lumbar spine and total hip)	Mandated at screening	Mandated at End of Treatment Core and End of Treatment Extension, unless EOT occurs less than 6 months before the scheduled Week 96 visit.

* For patients who discontinued study drug during Period 1.

All urine samples will be sent to the central laboratory designated by Novartis for assessment. During Period 1, once results are available, an alert (by email or fax) will be sent to the IE. The central laboratory and the IE will ensure that the sites and Novartis remain blinded to the results.

Starting from Week 14 in Period 2, UFC results will be sent directly by the central laboratory to the investigators.

7.2.1.1 Urinary Free Cortisol

The primary efficacy parameter, Urinary Free Cortisol (UFC), will be assessed using a central laboratory. UFC will be measured in two or three 24-hour urine samples (Table 7-1a, Table 7-1b, Table 7-2, and Table 7-3). Values from the individual samples for a visit will be averaged to obtain the mean UFC (mUFC) level. Urine creatinine levels will also be measured to ensure validity of the 24-hour collection.

Throughout the study, patients will collect the 24-hour UFC samples preferably on consecutive days according to Table 7-1a, Table 7-1b, Table 7-2, and Table 7-3 and will complete the patient diary. Patients are to bring both the urine samples and the patient diary to each study visit.

Screening (post washout): Three 24-hour UFC samples must be collected (preferably on consecutive days) and sent to central laboratory at least 14 days prior to day 1 in order to ensure that sufficient time is allowed for central laboratory results to become available. These samples will be used to assess eligibility of the patient. A repeated evaluation within the screening window is permitted for screening results out of the defined range. If the repeated laboratory result meets the criteria, that result may be used to determine eligibility. If the repeated laboratory result does not meet the criteria, the patient will be considered a screening failure.

Baseline: Three 24-hour UFC samples will be collected (preferably on consecutive days) within 7 days prior to first day of treatment to serve as baseline value.

Treatment period: Patients will collect two 24-hour UFC samples preferably over the 2 consecutive days immediately prior to the each visit, i.e. the last urine sample should be collected the day prior to the site visit (collection may end on the morning of the visit) as defined in Table 7-1a and Table 7-1b for Periods 1 and 2 (Core phase), and Table 7-2 for the optional Extension phase. Patients will collect three 24-hour UFC samples preferably on consecutive days immediately prior to the Week 12, Week 36, Week 48 and Week 12 Post-treatment follow-up visits. If only one UFC value is available at a visit, this value will be used for dose decision making only and not for mUFC based analysis.

7.2.1.2 Physical features of Cushing's disease

The following clinical signs (physical findings) of Cushing's disease will be assessed clinically for severity at time points defined in Table 7-1a, Table 7-1b, Table 7-2 and Table 7-3: facial rubor, hirsutism (female only), striae, supraclavicular and dorsal fat pads, proximal muscle wasting (atrophy), central (abdominal) obesity, and ecchymoses (bruising). These clinical signs are to be rated on a semi-quantitative scale as follows: 0=absent; 1=mild; 2=moderate; and 3=severe.

Physical features of Cushing's disease will also be documented by photography. A total of four photographs will be taken. Two photographs, one frontal and one lateral from the shoulders up will be taken to assess facial plethora (rubor), supraclavicular and dorsal fat pads. Two photographs, frontal and dorsal of the trunk with patient in standing position will be taken to assess striae, proximal muscle wasting (atrophy), central (abdominal) obesity, and ecchymoses (bruising). In order to maintain confidentiality, photographs will not be published without the explicit written consent of the patient. Photographs will be centrally collected and checked for quality by an imaging vendor. The quality checks will be detailed in the vendor manual.

If for cultural reasons, usual lifestyle, or other reasons, photographic assessments cannot be performed, this must be discussed with the sponsor on a case-by-case basis and sponsor approval will be required.

7.2.1.3 Bone mineral density assessments

Bone mineral density (BMD) of the lumbar vertebrae (L1-L4) and left total hip are to be measured using Lunar or Hologic DXA (dual-energy X-ray absorptiometry; DXA) instruments. A patient should be scanned on the same DXA instrument throughout the study. If a scan of the left proximal femur is not possible, then the right proximal femur can be used which is then to be used consistently throughout the study. Patients are to be positioned and scanning is to be performed according to the manufacturer's instructions and the imaging acquisition guidelines provided for this study. The image acquisition guidelines include detailed instructions on scanning methods, calibration of individual DXA machines and cross-calibration of DXA machines at different sites. The BMD results must be reported in actual density (gm/cm²) and standardized against the peak bone mass in a healthy young adult population (BMD T-score). Analysis and reporting of BMD results will be conducted centrally by the imaging vendor for this study. This assessment will be done as defined in [Table 7-1a](#), [Table 7-1b](#), [Table 7-2](#) and [Table 7-3](#). If EOT occurs less than 6 months before the scheduled Week 96 visit, MRI (or CT) and DXA is not mandatory at EOT.

Bone mineral density assessments will not be done in patients that are enrolled in Germany.

7.2.2 Safety and tolerability assessments

Safety will be monitored by assessing physical examination, vital signs, laboratory evaluations, radiological assessments, imaging assessments, cardiac assessments, as well as collecting of the adverse events at every visit. For details on AE collection and reporting, refer to [Section 8](#). The risk of suicide will be also collected and assessed as part of safety monitoring.

7.2.2.1 Physical examination

A complete physical examination will include the examination of general appearance, skin, neck (including thyroid), eyes, ears, nose, throat, lungs, heart, abdomen, back, lymph nodes, extremities, vascular and neurological. If indicated based on medical history and/or symptoms, rectal, external genitalia, breast, and pelvic exams will be performed. This will be conducted at visits according to [Table 7-1a](#), [Table 7-1b](#) and [Table 7-2](#).

Significant findings that were present prior to the signing of informed consent must be recorded in the Medical History page of the patient's eCRF. Significant new findings that begin or worsen after informed consent must be recorded on the Adverse Event eCRF.

7.2.2.1.1 Signs and symptoms of adrenal insufficiency

Signs and symptoms of adrenal insufficiency (AI) should be assessed at every study visit and / or contact according to [Table 7-1a](#), [Table 7-1b](#) and [Table 7-2](#). Signs and symptoms of AI are to be recorded on the Signs and symptoms of AI eCRF and in the AE eCRF during Period 1, and in the AE eCRF only during all other study periods.

Definition of signs and symptoms of AI ([Charmandari, et al 2014](#)):

- Symptoms: Nausea, vomiting, diarrhea, fatigue, asthenia, dizziness, syncope, decreased appetite, myalgia, arthralgia, and pyrexia
- Signs: hypotension, orthostatic hypotension, and tachycardia.

7.2.2.2 Vital Signs

Vital signs include blood pressure and pulse measurements, and body temperature will be assessed according to [Table 7-1a](#), [Table 7-1b](#) and [Table 7-2](#). Pulse and systolic and diastolic blood pressure will be measured using an automated validated device with an appropriately sized cuff according to the following sequence and times at each visit:

1. Supine: two separate recordings after the patient has been supine for a minimum of five minutes
2. Standing: one recording after the patient has been standing for 1 minute and another recording after the patient has been standing for 3 minutes.

These measurements will be used to assess the presence of orthostatic hypotension.

A drop in systolic blood pressure of ≥ 20 mmHg, or in diastolic blood pressure of ≥ 10 mmHg in the supine vs standing measurements, or presence of lightheadedness or dizziness is considered abnormal and should be recorded on the appropriate form (see section 7.2.2.1.1).

Vital sign assessments at screening may be repeated, if necessary, up to a maximum of 3 times.

7.2.2.3 Height and weight and waist circumference

Height in centimeters (cm) and body weight (to the nearest 0.1 kilogram [kg] in indoor clothing, but without shoes) will be measured. Body height will be measured at screening, and body weight and waist circumference will be measured at visits according to [Table 7-1a](#), [Table 7-1b](#) and [Table 7-2](#).

To measure waist circumference, patients should remove clothing from around the waist to ensure the measuring tape is correctly positioned. Using e.g. a cosmetic pencil, make a mark at the “natural waist” midway between the palpated iliac crest and the palpated lowest rib margin in the left and right mid-axillary lines. Place the non-stretchable tape evenly around the natural waist covering the left and right natural waist marks. The measurement scale should face outward, and there should be no twists in the tape. Ensure that the tape is just touching the skin but not compressing the soft tissue. Instruct patients to stand erect with abdomen relaxed, arms at sides, feet together, and weight divided equally over both legs.

7.2.2.4 Laboratory evaluations

Clinical laboratory analyses (hematology, chemistry, coagulation, urinalysis, thyroid panel and additional tests mentioned in [Table 7-4](#) below) are to be performed by the central laboratory.

At any time during the study, abnormal laboratory parameters which are clinically significant and require an action to be taken with study drug (e.g., require dose modification and/or interruption of study drug, lead to clinical symptoms or signs, or require therapeutic intervention), whether specifically requested in the protocol or not, will be recorded on the AE eCRF page. Laboratory data will be summarized using the CTCAE version 4.03 if applicable.

Table 7-4 Central Clinical laboratory parameters

Test Category	Test Name
Hematology	Hematocrit, Hemoglobin, Platelets, Red blood cells, White blood cells, RBC Morphology, Differential (Basophils, Eosinophils, Lymphocytes, Monocytes, Neutrophils, Bands, Other (absolute value preferred , %s are acceptable)
Chemistry	Albumin, Alkaline phosphatase, ALT, AST , Bicarbonate, Glucose, Calcium, Chloride, Creatinine, Creatine phosphokinase (CPK), Gamma-glutamyl-transferase (GGT), Lactate dehydrogenase (LDH), inorganic phosphorus, lipase, amylase, magnesium, potassium, sodium, Total Bilirubin, Direct Bilirubin, Indirect Bilirubin, Total Protein, Blood Urea Nitrogen (BUN) or Urea, Uric Acid
Urinalysis	Macroscopic Panel (Bilirubin, Blood, Glucose, Ketones, Leukocytes esterase, pH, Protein, Specific Gravity)
Coagulation	International normalized ratio (INR), Activated partial thromboplastin time (APTT)
Thyroid	Free T4, Thyroid-Stimulating Hormone (TSH)
Additional tests	Pregnancy test: serum (central lab testing) / Urine dipstick pregnancy testing (local lab testing) Additional hormones: Serum testosterone, estradiol, FSH Serum DHEAS, androstenedione and estrone Plasma renin Plasma ACTH Serum aldosterone, cortisol and 11-deoxycortisol Salivary cortisol (morning and late night)* Serum 11-deoxycorticosterone LH Other parameters: Fasting serum insulin, fasting plasma glucose and fasting lipid profile (including: Total Cholesterol, LDL, HDL, Triglycerides) HbA1c Hair cortisol

* Salivary cortisol samples will be collected within the following intervals: Late night samples between 10:00 pm and 11:00 pm and morning samples between 8:00 am and 10:00 am. Late night salivary cortisol samples will be collected with each 24-hr UFC collection (or with the last two 24-hr UFC collections closest to the next visit if 3 samples are being collected), and the morning salivary cortisol sample will be collected with the last 24-hr UFC collection.

Details on the collections, shipment of samples and reporting of results by the central laboratory are provided to investigators in the [\[Laboratory Manual\]](#).

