1.2.1.2.3 Overview of safety

In the clinical trials for the treatment of hypertension or primary hyperaldosteronism, osilodrostat was tolerated with the overall incidence of adverse events being similar to placebo. Adverse events (AEs) were generally of mild to moderate intensity. Both SAEs and discontinuations due to AE were infrequent, and were reported at a rate similar to placebo in the hypertension studies. The most common AEs across these studies were: headache, dizziness (including postural dizziness), nausea, diarrhea and fatigue. There were also AEs of hyperkalemia and impaired ACTH-stimulated cortisol response in these trials, which are consistent with the potential for hypocortisolism and hypoaldosteronism.

In Study [CLCI699C2201], in patients with Cushing's disease, safety data from the 10-week analysis also showed that osilodrostat was well tolerated with similar common adverse events to those in the hypertension trials, including: fatigue, nausea, vomiting, diarrhea, headache, dizziness, hypokalemia and muscle spasms.

In Part I of the study [LCI699C2201], all 12 patients (100%) experienced adverse events but these were generally mild to moderate in severity (NCI CTC grade 1 or grade 2). Fatigue, muscle cramps, dizziness and gastrointestinal events were the most common events suspected to be drug related. Four patients reported AEs consistent with cortisol and/or aldosterone withdrawal; dose reductions or temporary dose interruption in these patients improved the symptoms. There were no discontinuations related to study drug and no serious adverse events of suspected drug relationship.

In Part II, osilodrostat was generally well tolerated throughout the study. Of the 19 enrolled patients, 17 patients completed the 22 weeks treatment period with a median duration of exposure of 25.1 and 38.9 weeks in the Expansion cohort and Follow-up cohort, respectively. The safety findings identified in the interim analysis (data cut-off date: 23-Dec-2013) that was

performed after the last patient had completed 22 weeks of treatment in this ongoing study are summarized below.

Except for one patient in the Expansion cohort, all patients experienced AEs, grade 1/2 in most of the cases. Adrenal insufficiency, nausea, fatigue and increase levels of oxycorticosteroids, blood corticotrophin, and blood testosterone were the most common AEs suspected to be drug related (by PT).

Two patients experienced a total of 3 SAEs.

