6.2 Dose titration guidelines

6.2.1 Study Period 1: The double-blind, placebo-controlled period (Weeks 1-12).

For patients on osilodrostat arm, the IE is responsible for study drug dose titrations during Period 1, as the Investigators will not have access to UFC, serum cortisol, and other related laboratory results (as described in [Section 4.1](#)) that could disclose the randomized treatment assignment. The IE will determine the study drug dose once the mUFC level is available from scheduled study visits at Week 2, Week 5 and Week 8, and has access to following data:

- treatment allocation
- mUFC and individual 24-hour UFC values from the most recent study visit (see [Table 7-1a](#)), and mUFC values since the beginning of the trial (as reported by the central laboratory)
- other relevant laboratory data (i.e., serum cortisol, ACTH, and chemistry)
- data on the presence or absence of clinical signs and symptoms of adrenal insufficiency (AI; as recorded on the clinical signs and symptoms of AI eCRF page from the most recent study visit) (see [Section 7.2.2.1.1](#) for details).
- vital signs as recorded in the eCRF
- study drug doses since the beginning of the trial (as recorded on the Drug Administration Record (DAR) eCRF).

In order to maintain the study blind, communication from the IE to the investigator must be limited to communication of study drug dose decisions through the IRT system.

For patients in the placebo arm, a simulated dose titration sequence will be used to maintain the blind.

6.2.1.1 Dose up-titration during Period 1

The initial study drug dose in Period 1 is osilodrostat or placebo 2 mg b.i.d. The dose escalation sequence is: 5 mg b.i.d., 10 mg b.i.d. and 20 mg b.i.d. The IE will up-titrate the osilodrostat dose to the next dose in the sequence, based on the mUFC value until mUFC is normalized. While the goal is to normalize mUFC, decision to up-titrate dose will take into consideration the totality of the data available on each patient e.g. level of mUFC, rate of decrease of mUFC and tolerability of study drug (see [Section 6.3](#)).

Once mUFC is in the normal range (i.e., $mUFC \leq ULN$ and $\geq LLN$), the dose should be maintained, provided there are no safety concerns requiring a dose reduction or interruption (as described below and in [Section 6.3](#)).

6.2.1.2 Dose down-titration during Period 1

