The dose of study drug may be down-titrated or interrupted by the IE in patients with mUFC values $< LLN$ or close to LLN together with signs and/or symptoms of adrenal insufficiency. However, it is expected that the investigator will take immediate action to temporarily withhold study medication, without waiting for instructions from the IE, if their patient had suspected adrenal insufficiency, or any AE that requires replacement therapy with glucocorticoids (see

[Section 6.3.1](#) for details). In the event the investigator interrupts study drug, this information must be recorded in the eCRF as soon as possible, so that the IE can take this into account when selecting the next scheduled study drug dose.

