8.1.2 Laboratory test abnormalities

8.1.2.1 Definitions and reporting

Laboratory abnormalities that constitute an Adverse event in their own right (are considered clinically significant, induce clinical signs or symptoms, require concomitant therapy or require changes in study drug), should be recorded on the Adverse Events eCRF. Whenever possible, a diagnosis, rather than a symptom should be provided (e.g. anemia instead of low hemoglobin). Laboratory abnormalities that meet the criteria for Adverse Events should be followed until they have returned to normal or an adequate explanation of the abnormality is found. When an abnormal laboratory or test result corresponds to a sign/symptom of an already reported adverse event, it is not necessary to separately record the lab/test result as an additional event.

Laboratory abnormalities, that do not meet the definition of an adverse event, should not be reported as adverse events. A Grade 3 or 4 event (severe) as per CTCAE does not automatically indicate a SAE unless it meets the definition of serious as defined below and/or as per investigator's discretion. A dose hold or medication for the lab abnormality may be required by the protocol in which case the lab abnormality would still, by definition, be an adverse event and must be reported as such.

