2.8.1.2 Adverse events by time of onset

AEs will also be categorized by the time of onset, and separate summaries shown for defined time periods of the study.

The time periods used will be

- Baseline to Week 12
- Week 12 to Week 24
- Week 24 to Week 36
- Week 36 to Week 48
- Week 48 to Week 60
- Week 60 onwards

The denominator for each time period will be the number of patients still on the study at the start of that period. These summaries will be reported for

- Adverse events of Special Interest, regardless of study drug relationship, by category and preferred term
- Adverse events of Special Interest with suspected study drug relationship, by category and preferred term

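### In Period 1, asymptomatic abnormalities in the blinded hormone results cannot be recorded as adverse events, so biochemical hypocortisolism is under-ascertained in the placebo-controlled comparison

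*Protocol*

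**What the plan says.** There are two SAPs: the core SAP (released 01-Apr-2019) and the final SAP (released 01-Dec-2020).

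**Recording rule.** Protocol Section 7.2.2.4 covers results of this kind: "At any time during the study, abnormal laboratory parameters which are clinically significant and require an action to be taken with study drug". They go on the AE page, and a need for dose modification or interruption is among the examples given. Section 8.1.2.1 adds that where the protocol requires a dose hold or medication for a laboratory abnormality, "in which case the lab abnormality would still, by definition, be an adverse event and must be reported as such". Section 9.3 gives eCRF entry to investigator staff.

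**Blinding.** Protocol Sections 4.1 and 6.5.3 hide UFC, cortisol, ACTH, aldosterone, renin, sex steroids and the two 11-deoxy precursors from sites in Period 1, until the Core database lock is complete. Section 7.2.1 says "The central laboratory and the IE will ensure that the sites and Novartis remain blinded to the results".

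**Who acts on the result.** Section 6.2.1.2 says "The dose of study drug may be down-titrated or interrupted by the IE in patients with mUFC values" that are low or near the lower limit. Section 6.2.1 says "communication from the IE to the investigator must be limited to communication of study drug dose decisions through the IRT system".

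**Analysis.** Protocol Section 8.1.3.3 collects AESIs through routine AE reporting. Core SAP Section 2.8 compares safety by arm in the placebo-control period. Final SAP Section 2.8.1.2 tabulates "Adverse events of Special Interest, regardless of study drug relationship, by category and preferred term" in onset windows, the first being baseline to Week 12.

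**The concern.** The person who must record the event cannot see it, and the person who sees it has no stated way to record it. From Week 14 investigators see all results, so the same abnormality becomes reportable.

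Two things are at stake. First, Period 1 is the only randomised safety comparison. Suppression of cortisol below normal is a drug effect, so any shortfall should fall mainly on the osilodrostat arm and make the difference from placebo look smaller. Second, the final SAP's onset windows run across a change in what investigators can report.

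The issue is not remote. In Phase II Part II (Protocol Section 1.2.1.2.3), "Adrenal insufficiency, nausea, fatigue and increase levels of oxycorticosteroids, blood corticotrophin, and blood testosterone were the most common AEs" suspected to be drug related. Three of those six terms are hormone levels, and those hormones are blinded in Period 1 here.

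**Working it through.** The plan gives no figure for this, so the check sets the passages side by side. A scale illustration follows.

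**Can the rule be followed for an asymptomatic low mUFC in Period 1?**

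1. *Is a dose action on the laboratory value alone foreseen?* Yes. Section 6.2.1.2 leaves unclear whether symptoms are needed when mUFC is below the LLN. The Protocol summary and final SAP Section 1.1.2 treat a value below the LLN as sufficient. Table 6-1 has a row for persistent asymptomatic hypocortisolism, at the lowest dose only. Section 6.3.2 says low cortisol can occur without symptoms.
2. *Does the site see the value?* No (Sections 4.1, 6.5.3, 7.2.1).
3. *Can the site infer it from the dose change?* No. Placebo patients have mock down-titrations (Sections 2.2.2, 6.2.1.3).
4. *Can the IE, the central laboratory or the sponsor record it?* No such route is described.

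**Does another planned output count it?**

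- Core SAP Section 2.4.1.2 summarises reasons for dose reduction or interruption and lists dose changes with UFC. The site is not told that a low mUFC prompted an IE reduction, and a listing is not a by-arm count.
- Core SAP Section 2.8.3 plans low/normal/high shift tables for ungraded tests but does not name UFC or the hormones. Protocol Section 10.5.3.3 names hematology and biochemistry; final SAP Section 2.8.3 adds urinary tests. Protocol Table 7-1a lists UFC and the hormones as efficacy assessments.
- Core SAP Sections 2.7.2 and 2.7.8 give descriptive summaries of mUFC and cortisol, not counts below the LLN.
- Under core SAP Section 2.5.1, mUFC below the LLN also satisfies mUFC ≤ ULN, so such a patient counts as a complete responder.

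**Scale, as illustration.** Inputs: hypocortisolism in 4 of 12 Part I and 6 of 19 Part II patients, and one Part II dose reduction on biochemical evidence (Protocol Section 2.3); four Part I patients with symptoms suggesting glucocorticoid withdrawal (Section 8.1.3.2); 46 osilodrostat patients planned (core SAP Section 1.1).

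- Patient-courses: 12 + 19 = 31. Cases: 4 + 6 = 10, so 10/31 = 32%, or 10/31 × 46 = 14.8 patients.
- Lower figure, one documented biochemical case: 1/31 × 46 = 1.5.
- Upper figure, assuming the four Part I cases are the four with symptoms, leaving at most 10 − 4 = 6 biochemical only: 6/31 × 46 = 8.9.
- If the biochemical case is one of the ten, the recorded rate would be 9/31 = 29% at the lower figure and 4/31 = 13% at the upper, against 32%.

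Section 2.3 does not say whether that case is among the six from Part II. If it is additional, the upper figure becomes 7/31 × 46 = 10.4.

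**The case against.** The strongest reply is that most of what matters is still captured, and that the gap is the price of the blind.

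- Signs and symptoms of adrenal insufficiency go on a dedicated page and on the AE page in Period 1 (Protocol Section 7.2.2.1.1). The investigator may interrupt drug on suspicion, and may see an urgent serum cortisol in suspected acute adrenal insufficiency or crisis (Section 6.3.1).
- The precursor-related events named in Section 2.6 include changes in blood pressure, potassium, sodium and weight, edema, hirsutism and acne. None is on the blinded list.
- No dosing rule acts on ACTH, testosterone or precursors alone, so these would be AEs only if they otherwise qualified, for example as clinically significant. Section 1.2.1.2.2 calls such changes expected.
- The laboratory data are kept, and locked data can be changed with written authorisation (Section 9.4).
- The composition of the AESI groups is in a separate file, so whether they contain laboratory terms cannot be seen.

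All of this stands. A reader might infer that hypocortisolism and precursor events as a class cannot be reported in Period 1, or that the information is lost. The documents support neither. A reader might also attribute any rise in AESIs after Week 12 to unblinding of the laboratory results. Re-titration, dosing by investigators and a higher dose ceiling begin then too, so the cause could not be separated.

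The reply does not supply a recording route for an asymptomatic low mUFC on which the IE acts, or a planned by-arm count of it.

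**Conclusion.** The point holds for asymptomatic abnormalities in the blinded analytes. The firm case is mUFC or serum cortisol below the LLN that leads the IE to reduce or interrupt study drug; the AE rule cannot be followed for it in Period 1. Hormone and precursor elevations are a weaker case, limited to those that would be considered clinically significant. Purely biochemical hypocortisolism is therefore under-ascertained in the controlled AE comparison, and onset windows before and after Week 12 are not ascertained alike. The effect on AESI tables also assumes that those groups include laboratory terms.

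The size cannot be fixed from the documents. The figure of about 1 to 9 of 46 osilodrostat patients assumes that Phase II rates carry over and, for the upper end, that the two sets of four Part I patients are the same people. Phase II differed in duration and doses, and four of its patients count in both parts. A much larger share of biochemical-only cases, such as three quarters, would not fit those counts under the same assumption. The point does not rest on the number, and neither the primary nor the key secondary test is affected.

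**What to change.** 1. **Core SAP Sections 2.8.1.1 and 2.8.3.** Specify a by-arm Period 1 table from unblinded central-laboratory and dosing data, placed beside the AESI table. Count patients with any mUFC or serum cortisol below the LLN; with ACTH, testosterone, 11-deoxycortisol or 11-deoxycorticosterone above the ULN that is new or worsened from baseline; and with any IE reduction or interruption following mUFC below the LLN. The baseline condition matters because ACTH may already be raised at entry in both arms.
2. **Final SAP Section 2.8.1.2.** Show AESIs by onset with and without laboratory-defined preferred terms, and note that reporting of these terms changes when results are unblinded.
3. **Protocol Sections 7.2.2.4 and 8.1.2.1.** State that in Period 1 the AE rule applies to results available to the investigator, and reconcile these sections with 4.1, 6.2.1 and 6.5.3. Table 6-1 needs the same reconciliation: for Weeks 1 to 12 it refers the investigator to testosterone levels, and its recovery guideline to mUFC, both of which are blinded then.

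The cost is programming on data already collected and a few lines of text. The downside is one more table and possibly a less favourable Period 1 hypocortisolism figure. The final SAP says the core report has been written, so a table added now should be labelled as added after unblinding.
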